2.4 Follow-up Visits

At least three follow-up visits (X1, X2 and X3) are required for all subjects. Visit X1 will take place 30 days (+/- 1 week) after the last dose of study medication in the cycle where nivolumab was discontinued, visit X2 will take place 8 weeks (+/- 1 week) after last dose of nivolumab was administered and visit X3 will take place 15 weeks (+/- 1 week) after last dose of nivolumab was administered. The duration of the follow-up period up to the X3 visit is equal to approximately 5 half-lives of nivolumab. If additional X follow-up visits are required due to ongoing study drug- related toxicity, they should take place every 8 weeks (+/- 1 week) until study drug-related toxicity has resolved, stabilized or been deemed irreversible.

2.5 Survival Follow-up

After follow-up visits, study subjects will be contacted every 3 months for survival data. Other potential data such as the subjects' follow-up treatment or care may be requested during these contacts. The contacts can be via telephone or correspond with disease assessment visits, if

subject went off treatment for other than progressive disease, or other scheduled visits.

2.6 Subsequent therapy

Subjects for whom treatment is discontinued should be treated according to clinical circumstances and should be managed at the local clinician's discretion.

2.7 Concomitant Treatments

2.7.1 Prohibited and/or Restricted Treatments

The following medications are prohibited during the study:

- Immunosuppressive agents (except to treat a drug-related adverse event). Systemic corticosteroids > 10 mg daily prednisone equivalent (except as stated in Section 2.7.3 below or to treat a drug-related adverse event).
- Any concurrent antineoplastic therapy (ie, chemotherapy, hormonal therapy, immunotherapy, radiation therapy except for palliative radiation therapy surgical resection except for palliative surgical resection).
- Supportive care for disease-related symptoms may be offered to all subjects on the trial.
- Any concurrent meds should be evaluated for being absolutely necessary. Particularly drugs with potential liver toxicity should be avoided if possible

2.7.2 Other Restrictions and Precautions

Palliative (limited-field) radiation therapy and palliative surgical resection are permitted, if the following criteria are met:

- The subject will be considered to have progressed at the time of palliative therapy and must meet criteria to continue with treatment beyond progression. (Section 3.5)

2.7.3 Permitted Therapy

Subjects are permitted to use topical, ocular, intra-articular, intranasal, and inhalational corticosteroids (with minimal systemic absorption). Physiologic replacement doses of systemic corticosteroids are permitted, up to 10 mg/day prednisone equivalents. A brief course of corticosteroids for prophylaxis (eg, contrast dye allergy) or for treatment of non-autoimmune conditions (eg, delayed-type hypersensitivity reaction caused by contact allergen) is permitted. Concomitant medications are recorded at baseline and throughout the treatment phase of the study in the appropriate section of the case report form (CRF). All medications (prescriptions

or over the counter medications) continued at the start of the study or started during the study and different from the study drug must be documented in the concomitant therapy section of the CRF.

2.8 Discontinuation of Subjects following any Treatment with Study Drug

Subjects MUST discontinue investigational product (and non-investigational product at the discretion of the investigator) for any of the following reasons:

- Subject's request to stop study treatment
- Any clinical adverse event, laboratory abnormality or intercurrent illness which, in the opinion of the investigator, indicates that continued participation in the study is not in the best interest of the subject
- Protocol defined disease progression (subjects may be permitted to continue treatment beyond initial disease progression see Section 3.5)
- Loss of ability to freely provide consent through imprisonment or involuntarily incarceration for treatment of either a psychiatric or physical (eg, infectious disease) illness
- Additional protocol specified reasons for discontinuation (see Section 3.4.5)

In the case of pregnancy, the study subject will be permanently discontinued in an appropriate manner. All subjects who discontinue study drug should comply with protocol specified follow-up procedures as outlined in Section 3 (Study Assessment and Procedures). The only exception to this requirement is when a subject withdraws consent for all study procedures including post-treatment study follow-up or loses the ability to consent freely (ie, is imprisoned or involuntarily incarcerated for the treatment of either a psychiatric or physical illness).

If study drug is discontinued prior to the subject's completion of the study, the reason for the discontinuation must be documented in the subject's medical records and entered on the appropriate CRF page.

2.9 Post Study Drug Study Follow up

In this study, **overall response rate** is a key endpoint of the study. Post study follow-up is of critical importance and is essential to preserving subject safety and the integrity of the study. Subjects who discontinue study drug must continue to be followed for collection of outcome

and/or survival follow-up data as required and in line with Section 3 (Study Assessment and Procedures) until death or the conclusion of the study.

2.9.1 Withdrawal of Consent

Subjects who request to discontinue study drug will remain in the study and must continue to be followed for protocol specified follow-up procedures. The only exception to this is when a subject specifically withdraws consent for any further contact with him/her or persons previously authorized by subject to provide this information. Subjects should notify the investigator of the decision to withdraw consent from future follow-up **in writing**, whenever possible. The withdrawal of consent should be explained in detail in the medical records by the investigator, as to whether the withdrawal is from further treatment with study drug only or also from study procedures and/or post treatment study follow-up, and entered on the appropriate CRF page. In the event that vital status (whether the subject is alive or dead) is being measured, publicly available information should be used to determine vital status only as appropriately directed in accordance with local law.

2.9.2 Lost to Follow-Up

All reasonable efforts must be made to locate subjects to determine and report their ongoing status. This includes follow-up with persons authorized by the subject as noted above. Lost to follow-up is defined by the inability to reach the subject after a minimum of three documented phone calls, faxes, or emails as well as lack of response by subject to one registered mail letter. All attempts should be documented in the subject's medical records. If it is determined that the subject has died, the site will use permissible local methods to obtain the date and cause of death.

The site staff and representative will consult publicly available sources, such as public health registries and databases, in order to obtain updated contact information. If after all attempts, the subject remains lost to follow-up, then the last known alive date as determined by the investigator should be reported and documented in the subject's medical records.

TREATMENT PLAN/THERAPEUTIC INTERVENTION

3.1 Treatment Plan

3.1.1 Study Drug

Study drug includes both Investigational (Investigational Medicinal Product) and Non-Investigational Therapy and can consist of the following:

- All products, active or placebo, being tested or used as a comparator in a clinical trial
- Study required premedication, and other drugs administered as part of the study that are critical to claims of efficacy (eg, background therapy, rescue medications)
- Diagnostic agents: (such as glucose for glucose challenge) given as part of the protocol requirements must also be included in the dosing data collection

Nivolumab 100 mg (10 mg/mL) will be packaged in an open-label fashion. Five or ten nivolumab 10 mL vials will be packaged within a carton. The vials are not subject or treatment group specific. Each site will complete a drug request form and submit the form to BMS to receive the medication and obtain re-supply.

Ipilimumab will be supplied as a sterile, preservative-free solution in 40 mL vials at a concentration of 5 mg/mL. Each vial contains a concentrated solution with the equivalent of 200 mg of ipilimumab.

Table 3. Product Description: Treatment Period

Product Description / Class and Dosage Form	Potency	Primary Packaging (Volume)/ Label Type	Secondary Packaging (Qty) /Label Type	Packaging/Appearance	Storage Conditions (per label)
Nivolumab Solution for Injection ^a	100 mg (10 mg/mL)	10 mL per vial/	5 vials per carton/ Open-label	Clear to opalescent colorless to pale yellow liquid. May contain particles	2° to 8°C. Protect from light and freezing
Ipilimumab	200 mg (5 mg/mL)	40 mL per vial/Openlabel	4 vials per carton/Open-label	Clear to opalescent colorless to pale yellow liquid. May contain particles	2° to 8°C. Protect from light and freezing

^a Nivolumab is labeled as BMS-936558-01 Solution for Injection.

3.1.2 Investigational Products

An investigational product, also known as investigational medicinal product (IMP) in some regions, is defined as pharmaceutical form of an active substance or placebo being tested or used as a reference in a clinical study, including products already with a marketing authorization but used or assembled (formulated or packaged) differently than the authorized form, or used for an unauthorized indication, or when used to gain further information about the authorized form.

The investigational product should be stored in a secure area according to local regulations. It is the responsibility of the investigator to ensure that investigational product is only dispensed to study subjects. The investigational product must be dispensed only from official study sites by authorized personnel according to local regulations.

In this protocol, investigational products are:

- Nivolumab (BMS-936558)
- Ipilimumab

3.1.3 Non-investigational Product

Other medications used as support or escape medication for preventative, diagnostic, or therapeutic reasons, as components of the standard of care for a given diagnosis, may be considered as non-investigational products.

In this protocol, non-investigational product(s) is/are: medications used to treat nivolumab or ipilimumab infusion-related reactions (eg, steroids, anti-emetics); these non-investigational products should be sourced by the investigator sites if available and permitted by local regulations.

3.1.4 Storage and Dispensing

The product storage manager should ensure that the study drug is stored in accordance with the environmental conditions (temperature, light, and humidity) as determined by BMS. If concerns regarding the quality or appearance of the study drug arise, the study drug should not be dispensed and contact BMS and the principal investigator immediately.

If stored in a glass front refrigerator, vials should be stored in the carton. Recommended safety measures for preparation and handling of nivolumab and ipilimumab include laboratory coats and gloves.

Investigational product documentation must be maintained that includes all processes

STU072016-044, [name], FormA-ResearchProtocol-V7.0-09.30.19, Mod_14, 10-23-19 (2)

Page 30 of 99 (BMS CA209-444) V. V6.0 date March 1, 2019

This material is the property of the [UTSW Simmons Cancer Center](#). Do not disclose or use except as authorized in writing by the study sponsor.

required to ensure drug is accurately administered. This includes documentation of drug storage, administration and, as applicable, storage temperatures, reconstitution, and use of required processes (eg, required diluents, administration sets).

Infusion-related supplies (eg, IV bags, in-line filters, 0.9% NaCl solution) should be purchased locally if permitted by local regulations.

For nivolumab and ipilimumab, please refer to the current version of the Investigator Brochures and/or pharmacy reference sheets for complete storage, handling, dispensing, and infusion information.

Nivolumab is to be administered as an approximately 60-minute IV infusion. At the end of the infusion, flush the line with a sufficient quantity of normal saline.

Ipilimumab is to be administered as an approximately 30-minute IV infusion. At the end of the infusion, flush the line with a sufficient quantity of normal saline or 5% dextrose solution.

When both study drugs are to be administered on the same day, separate infusion bags and filters must be used for each infusion. Nivolumab is to be administered first.

3.2 Timing of Dose for Each Subject and Duration of Therapy

Table 4. Schedule for SBRT

	Week 1 D1	Week 2	Week 3	Week 4 D1	Week 5	Week 6
SBRT		5 fractions of 10 Gy				

Table 5. Dosing Schedule for Cycle 1 and Cycle 2

1 cycle = 6 weeks						
	Week 1	Week 2	Week 3	Week 4	Week 5	Week 6
Nivolumab 3 mg/kg IV + Ipilimumab 1 mg/Kg IV	Day 1 Nivolumab 3 mg/kg IV + Ipilimumab 1 mg/Kg IV			Day 1 Nivolumab 3 mg/kg IV + Ipilimumab 1 mg/Kg IV		

Table 6. Dosing Schedule for Cycle 3 and Beyond (up to 2 years) every 4 weeks

1 cycle = 8 weeks

	Week 1		Week 5			
	Day 1 Nivolumab 480 mg IV		Day 1 Nivolumab 480mg IV		480mg IV	

When nivolumab and ipilimumab are to be administered on the same day, separate infusion bags and filters must be used for each infusion. Nivolumab is to be administered first. The second infusion will always be ipilimumab, and will be administered at least 30 minutes after completion of the nivolumab infusion.

Ipilimumab may be diluted in 0.9% Sodium Chloride Solution or 5% Dextrose solution.

Nivolumab may be diluted in 0.9% Sodium Chloride Solution or 5% Dextrose solution.

The dosing calculations should be based on the actual body weight. If the subject's weight on the day of dosing differs by > 10% from the weight used to calculate the dose, the dose must be recalculated. (The weight used to calculate the dose should always be the most recently recorded weight). All doses should be rounded to the nearest milligram. There will be no dose modifications allowed.

During cycles 1 and 2, subjects may be dosed no less than 19 days from the previous dose of drug. Starting from cycle 3, subjects may be dosed no less than 26 days from the previous dose of drug. Patients may be dosed up to 3 days after the scheduled date if necessary or 2 days prior to expected date. Treatment compliance will be monitored by drug accountability as well as the subject's medical record and CRF.

Maintenance nivolumab will be allowed up to 2 years from the start of treatment.

3.3 Stereotactic Body Radiation Therapy

Prior to entry into the protocol, all patients need to be discussed with [name] (JHU), [name] (UTSW) or co-investigator Radiation Oncologist from the Radiation Therapy Department to determine eligibility/feasibility for SBRT. The cancer lesion(s) to be radiated should be determined by the Radiation Oncologist in collaboration with the Principal Investigator/Medical Oncologist using the criteria stated below.

3.3.1 Lesion selection criteria and dosing

The most common sites of involvement with metastatic RCC are lung (45%), bone (29%), lymph node (22%), liver (20%), and adrenal (9%)¹. Dosing, patient setup/immobilization, and dose constraints for lung sites will be in accordance with established experience specific to

STU072016-044, [name], FormA-ResearchProtocol-V7.0-09.30.19, Mod_14, 10-23-19 (2)

Page 32 of 99 (BMS CA209-444) V. V6.0 date March 1, 2019

This material is the property of the [UTSW Simmons Cancer Center](#). Do not disclose or use except as authorized in writing by the study sponsor.

those sites. Bone and lymph node sites will be treated and dosed in accordance with their anatomic location (extremity, thorax, or abdomen/pelvis) and surrounding dose-sensitive structures. The gross target volume (GTV) for SBRT will be a minimum of 1cm in short-axis diameter (in order to help assure an adequate volume of tumor cells for immune stimulation), and a maximum of 5cm in long-axis diameter. Liver lesions will not be considered for SBRT for patients on the protocol, as this could potentially lead to higher rates of liver failure and/or autoimmune hepatitis in the setting of concomitant immunotherapy.

Five fractions of SBRT at 10 Gy per fraction will be delivered within the first 3 weeks after the initiation of nivolumab and ipilimumab. Given the parallel goals of radiation of enhancing antitumor immune response and stimulating auto-vaccination (rather than to treat all known tumor tissue), as well as maintaining consistency in target dose prescription for purposes of analysis, the planning target volume and treatment margins may be defined in a manner which may involve potentially less than complete prescription dose coverage of the involved tumor. A working hypothesis of the trial is that optimal immune stimulation will occur with an ablative dose of radiation; the most robust dose-response relationships for SBRT come from the lung SBRT experience, where a biologically equivalent dose (BED) of approximately 100 Gy (equivalent to 10 Gy x 5 fractions) has been shown to be a threshold dose for optimal local control^{2,3}

If all relevant normal tissue constraints cannot be met while treating the entire metastatic focus, then planned target volume (PTV) margins will be modified downward in an iterative process to a minimum of 0mm (from GTV) in order to achieve normal tissue constraints. If normal tissue constraints still cannot be met, then consideration will be given to treating another lesion if a suitable alternative exists. If no suitable alternative target exists, then an **nPTV** will be generated which impinges upon the GTV in areas of proximity to critical normal tissues, until all protocol-specific SBRT tissue constraints have been met. For example, if the entire GTV can not be treated with 5 x 10 Gy because of surrounding normal tissue constraints, then only part of the gross target volume can be exposed to 5 x 10 Gy while the surrounding margin receives 5 x 8 Gy. Liver lesions will not be considered as a radiated target.

3.3.2 Simulation procedure

Patients will undergo simulation and immobilization in accordance with site-specific protocols established in the Dept. of Radiation Oncology.

Patients being treated to lung/thoracic or abdominal lesions will have respiratory movement of the target volume accounted for either with 4D-CT scanning or with Active Breathing Control (ABC) and inspiratory breath hold. Patients with greater than or equal to 5 mm of breathing

STU072016-044, [name], FormA-ResearchProtocol-V7.0-09.30.19, Mod_14, 10-23-19 (2)

Page 33 of 99 (BMS CA209-444) V. V6.0 date March 1, 2019

This material is the property of the [UTSW Simmons Cancer Center](#). Do not disclose or use except as authorized in writing by the study sponsor.

motion identified on 4D-CT should have ABC performed to minimize breathing motion. All other patients will have an Internal Target Volume (ITV) delineated using end-inspiratory and end-expiratory phases of the 4D-CT scan. A wingboard and/or alpha cradle may be utilized for patient positioning. Patients who have target volumes in close proximity to the upper GI tract (stomach, duodenum, small bowel) shall be instructed to be NPO for 3 hours prior to simulation and each daily treatment.

IV contrast should be utilized during CT simulation for patients with targets in the mediastinum. Patients being treated to pelvic lesions will be positioned with the Combifix device. Bladder filling (patient instructed to drink 30 oz. of water prior to simulation) is to be utilized if doing so will help eliminate or minimize small bowel from the treatment field.

For extremity lesions, immobilization with alpha cradle and/or Vac-Loc bags will be utilized. CT simulation will be performed with minimum 3mm slice thickness. MRI simulation may be utilized if target volume or normal anatomy delineation will be enhanced with its use. Diagnostic MRI scans may also be utilized to provide complementary anatomic information to CT simulations. MRI and CT simulation images will be fused using either Pinnacle or Velocity. The target volume (PTV or nPTV) for centrally located or mediastinal sites should not directly involve critical structures such as central bronchial tree (within 2cm of carina or hilum, as defined in RTOG 0813), esophagus, great vessels, or brachial plexus.

3.3.3 Target delineation

Spinal metastases may involve vertebral body alone, vertebral body and pedicle, or posterior elements only (as defined in NRG-BR-001). For each of these metastases, GTV delineation will include at a minimum the involved vertebral body and both pedicles, or the involved posterior elements and both pedicles.

Other targets will be delineated primarily based on CT simulation images, using the windowing settings specific for the anatomic location within which the target is contained. Additional imaging modalities such as MRI may be utilized at the radiation oncologist's discretion; rigid image registration is recommended if utilizing complementary imaging modalities in addition to CT simulation scans.

3.3.4 Normal tissue delineation and constraints

The following normal tissue delineation definitions are for purposes of consistency in those cases where ambiguity could potentially lead to inter-individual variations in contouring, and to adhere to well-defined generally accepted SBRT practice when available.

Spinal cord will be contoured based on the bony limits of the spinal canal, starting at least 10 cm above the superior extent of the PTV and continuing on every CT slice to at least 10 cm below the inferior extent of the PTV.

Cauda equina is defined as beginning at the conus (usually L1 or L2) and including the entire spinal canal to the filum terminale in the sacrum.

Sacral plexus will include the nerve roots beginning at L5 and extending to S3 bilaterally from neuroforamina to the coalescing of nerves at the obturator internus.

Esophagus is to be defined to include all layers from mucosal to adventitia, starting at least 10cm cranial and caudal to the extent of PTV.

Brachial plexus is to be contoured if target volume (PTV) is within 10 cm, using the technique as described by Hall et al⁴. It originates from nerves exiting neuroforamina from C5 to T2, and commonly defined on CT using subclavian and axillary vessels as surrogate structures.

Heart will be contoured including the pericardial sac. The superior aspect (or base) for purposes of contouring will begin at the level of the inferior aspect of the aortic arch (i.e. aortopulmonary window) and extend inferiorly to the apex of the heart.

Trachea and proximal bronchial tree will be defined as two structures; distal 2cm of trachea will be included in what is defined as proximal bronchial tree. Proximal bronchial tree will include the caudal 2cm of distal trachea plus proximal airways bilaterally as defined by Timmerman et al⁵ / RTOG 0813.

Lungs will be contoured separately as well as combined into a single structure for DVH purposes. GTV and trachea / proximal bronchial tree are to be excluded.

Skin is to be defined as the outer 5mm of body surface.

Great vessels (aorta, vena cava) will be contoured including entire thickness to the adventitia. Contours should extend from 10cm caudal to 10cm cranial from extent of PTV.

Duodenum will be defined from stomach, to where the superior mesenteric artery crosses over the 3rd part of duodenum.

Small bowel will be defined from duodenum (see above) to ileocecum. If small bowel and large bowel cannot be delineated with confidence, then the more generous contour should be utilized.

Large bowel will be defined from ileocecum to rectum (including sigmoid).

Rectum is to be defined from the peritoneal reflection cranially, typically extending 12-15 cm from anal verge to the valve of Houston, located approximately at level of S3. Caudal extent is at the junction with the anal canal, defined on axial CT at approximately level of bottom of ischial tuberosities.

Renal hilum will be contoured where renal vessels and renal pelvis are adjacent as they enter/exit the kidney.

Ureter is to be contoured from 10cm cranial to 10cm caudal to extent of PTV, and terminates at renal hilum and vesicoureteral junction, respectively.

Bile ducts are identified by portal vein from its juncture with the splenic vein to its right and left bifurcation in the liver as a surrogate.

Liver is entire liver minus GTV.

Kidneys will be defined in their entirety, but excluding the pelvis / collecting system.

Penile bulb is best delineated on MRI images, but can be visualized on CT if MRI unavailable. As defined by Wallner et al⁶, it is to be contoured as the cranial portion of the corpus spongiosum, between the corpora cavernosal and beneath the genitourinary diaphragm.

Normal tissue constraints

The dose will be prescribed to the minimal isodose line that completely covers the GTV (or ITV if applicable) plus a 0-5 mm margin to create a planning target volume (PTV). In order to achieve normal tissue dose constraints, PTV margins may be utilized which may not encompass the entire target volume with setup uncertainty and anatomic motion; PTV margins may be utilized which are negative (i.e. PTV smaller than GTV volume) in order to achieve protocol-specified doses while respecting normal tissue tolerances; such PTV volumes will be termed 'nPVT'. All relevant adjacent normal structures including but not limited to the heart, esophagus, aorta, spinal cord, kidneys, rectum, bowel, liver, and stomach within 5 cm of the GTV will be identified for the purpose of limiting incidental radiation to these structures.

Dose heterogeneity within the PTV may be high, and within the paradigm of SBRT is considered acceptable without constraints. The dose to any tissue outside of the PTV should not exceed 5% of the prescription dose.

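### The 5% limit on dose outside the PTV (3.3.4) contradicts the protocol's own partial-coverage example (3.3.1), which gives the surrounding margin 80% of prescription

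*Combined protocol and SAP*

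**What the plan says.** Section 3.3.1 (Lesion selection criteria and dosing) sets the prescription: "Five fractions of SBRT at 10 Gy per fraction will be delivered within the first 3 weeks" after the start of nivolumab and ipilimumab.

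The same section gives an ordered fallback for lesions where normal tissue constraints cannot be met with the whole metastasis treated. First, PTV margins are reduced, down to 0 mm from the GTV. Second, another lesion is considered. Third, only if there is no suitable alternative, an nPTV "will be generated which impinges upon the GTV in areas of proximity to critical normal tissues", until the constraints are met. As an illustration, it says that "only part of the gross target volume can be exposed to 5 x 10 Gy while the surrounding margin receives 5 x 8 Gy".

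Section 3.3.4 (Normal tissue delineation and constraints) allows the same device: "PTV margins may be utilized which are negative (i.e. PTV smaller than GTV volume"), and it names such reduced volumes with the nPTV label (spelled slightly differently there). It leaves dose inside the target unconstrained: "Dose heterogeneity within the PTV may be high, and within the paradigm of SBRT is considered acceptable without constraints". The next sentence limits dose outside the target: "The dose to any tissue outside of the PTV should not exceed 5% of the prescription dose".

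Neither section states an exception to that last sentence.

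**The concern.** The two sections appear to give incompatible instructions for the same plan. One illustrates a margin treated to a high dose around a reduced target. The other limits all tissue outside the target to a small fraction of prescription.

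This is an internal inconsistency in a limit on delivered radiation, so it bears on patient safety and on what treatment is actually given:

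- Safety and tolerability is a primary endpoint (2.1), and section 3.9 anticipates additive toxicity in irradiated lung and bowel.
- Section 3.3.1 itself stresses a consistent target dose for purposes of analysis. The two participating sites could resolve the conflict differently.
- Section 8.1 requires the study to be run as the protocol describes, and section 8.3 makes departures that put subjects at risk or affect the data reportable within 5 working days. A planner who uses the example departs from 3.3.4. A planner who applies 3.3.4 cannot use the example.
- Unsuitability for SBRT is an exclusion criterion (2.3.2), so an unclear planning limit could in principle affect who is judged eligible.

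**Working it through.** The 5% is a stated limit with no derivation in the documents, so there is no figure to reproduce. The check sets the limit against the example's dose and then asks whether the margin is really outside the PTV.

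**Inputs**

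- Prescription: 5 fractions x 10 Gy (3.3.1).
- Limit outside the PTV: 5% of prescription, any tissue (3.3.4).
- Margin dose in the partial-coverage example: 5 fractions x 8 Gy (3.3.1).

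**Dose arithmetic**

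1. Prescription = 5 x 10 = 50 Gy.
2. Limit = 0.05 x 50 = 2.5 Gy in total, or 0.05 x 10 = 0.5 Gy per fraction.
3. Margin dose = 5 x 8 = 40 Gy.
4. Margin as a share of prescription = 40 / 50 = 80%.
5. Margin relative to the limit = 40 / 2.5 = 16.

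**Sensitivity to the prescription.** Sections 1.5 and 1.8 describe 8 to 10 Gy per fraction, so one could take 5 x 8 = 40 Gy as the prescription. The limit would then be 0.05 x 40 = 2.0 Gy, and the margin would be 40 / 2.0 = 20 times the limit. The choice of prescription does not remove the conflict.

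**Is the margin outside the PTV?**

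1. Section 3.3.4 defines the reduced volume as a PTV smaller than the GTV, and section 3.3.2 refers to the PTV or nPTV as the target volume. In a reduced-target plan, the nPTV is therefore the PTV.
2. Section 3.3.1 says the nPTV is formed by cutting into the GTV near critical normal tissue. The part cut away is GTV that is no longer in the target.
3. In the example, part of the GTV gets the full 5 x 10 Gy and the margin around that part gets 5 x 8 Gy. The natural reading is that the full-dose part is the nPTV and the margin is what was cut away.
4. The margin is then outside the PTV, and the limit in 3.3.4, which applies to any tissue, covers it.

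So a plan built on the example delivers 40 Gy where 3.3.4 says 2.5 Gy should not be exceeded.

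**The case against.** Five points can be made on the other side.

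**The limit may be meant for normal tissue only.** It sits under a normal-tissue subheading and follows text about limiting incidental dose to listed organs. Section 3.3.4 also excludes GTV from the lung and liver contours, so it does separate tumor from normal tissue. In the example, the region denied full dose is tumor. This reading is arguable, but the sentence says any tissue and makes no exception for GTV.

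**The 5 x 8 Gy margin may be a lower-dose part of the target.** Section 3.3.1 does not say outright that the margin lies outside the nPTV, so its position is an inference. It is nevertheless the more natural reading, because the nPTV is described as cutting into the GTV.

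**The 5 x 8 Gy is an illustration at the end of a fallback sequence.** This stands, and it sets the scope. A reader might infer that every nPTV plan, or every patient planned with an nPTV, breaks 3.3.4. The documents do not support that: 5 x 8 Gy is offered as an example, not prescribed for all such plans.

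**Safeguards exist.** The limit is worded as a recommendation, and section 3.3 requires each patient to be discussed with a radiation oncologist before entry. That makes mechanical application less likely, but it does not correct the text. Nothing in the documents shows that anyone would be turned away from SBRT because of this sentence, so the eligibility consequence is a possibility only.

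**Context may be missing.** The text refers to protocol-specific constraints, but no numerical organ table appears in the copy available. A table may have been lost in conversion. There is no positive sign that one qualified the 5% sentence, so this carries little weight.

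**Conclusion.** The inconsistency is real. A plan that follows the partial-coverage example in 3.3.1 gives the margin 40 Gy against a limit of 2.5 Gy in 3.3.4: 80% of prescription against 5%, a factor of 16.

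The conclusion rests on two readings: that the margin in the example lies outside the nPTV, and that the limit means any tissue, as it says. Both are the plainer readings. If either fails, the text still does not tell a planner so.

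The scope is narrow. The clash is shown only for nPTV plans of the kind in the example, and the documents do not allow the number of patients to be estimated.

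Two further inferences should be resisted. A reader might infer that tissue next to any PTV must also exceed the limit, so that full-coverage plans fail too. The documents give no dose fall-off figures, so that is not shown. A reader might also take the 5% for an obvious slip and supply the intended number. It may be a slip, but the documents do not show what was meant.

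The sample size, the Simon two-stage boundaries, the error rates and the Bayesian safety rule are unaffected.

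**What to change.** Reconcile sections 3.3.1 and 3.3.4. The radiation oncology leads should confirm in writing:

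1. the figure intended for the limit outside the PTV;
2. the region and tissue to which it applies;
3. whether it covers GTV left outside an nPTV, including the margin in the 3.3.1 example.

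Both sections should then state the same rule, with any exception written out. The spelling of the nPTV label in 3.3.4 can be aligned at the same time. Which dose or limit is right is for the radiation oncology leads to decide; none is proposed here.

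The cost is one wording correction to the protocol, notified to both sites. No statistical section needs to change.
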